12.3 Power Analysis

This study has been designed to provide adequate power to address the primary hypothesis and corresponding analysis. Significant placebo effects have been found in many clinical trials of pharmacologic interventions for motor symptoms in PD. However, a recent meta-analysis found no significant placebo effect associated with sham rTMS on short or long-term changes in UPDRS in PD.¹⁶ Given that there are no prior studies from which to estimate treatment or placebo effects associated with taVNS in PD, we powered our study to detect a clinically meaningful change of -3.25 on the UPDRS,¹⁷ with treatment taVNS. assumed a small and statistically non-significant change of -1 on the UPDRS with sham taVNS, and a standard deviation (pooled) of 2.0. At 80% power and alpha=.05, using a two-tailed t-test for difference in means, the total sample size required is 26 (13 per group). Prior studies in this clinic have found attrition to be about 10% for short-duration clinical trials. Accordingly, a sample of 35 participants will be enrolled.

13. Data, safety, and quality assurance monitoring

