Transcutaneous auricular VNS (taVNS): Although cervical VNS is relatively safe, the risks involved in surgical implantation as well as its high cost (about \$30-50k) make it less appealing and less available as a study modality. Recently, it has been shown that VNS can be administered non-invasively through stimulating the auricular branch of the vagus nerve located in the ear¹¹⁻¹³ with a transcutaneous electrical nerve stimulation (TENS) device. Our collaborators ([name] et al.) in the MUSC Brain Stimulation Lab conducted initial safety and feasibility trials of transcutaneous auricular VNS (taVNS) in healthy adults. In these studies, there were no adverse effects of taVNS observed. Their work validates ideal parameters for delivering taVNS, suggesting that one-minute taVNS periods at 200% perceptual threshold delivered at 500 μ s 25Hz are safe and tolerable and produce regional brain changes consistent with activating the vagus nerve related brain regions involved in neuroplasticity.¹³ The same group developed and conducted a concurrent taVNS/fMRI trial and demonstrated that the neurobiological effect of taVNS mimics that of cervically implanted VNS and targets several cortical and subcortical vagus afferent pathway targets. It additionally suggested that taVNS for short time periods activates the vagus nerve (10-25Hz, average 1.8mA). No rapidly accelerated or sustained drops

in HR were seen during the one-minute taVNS stimulation periods. A follow-up study determined that the optimal parameter to modulate the parasympathetic response via taVNS was 500µs pulse width, 10 & 25Hz for 60s duration.¹³

The significance of this study lies in the novelty of stimulating the vagus nerve non-invasively, in order to increase LC-NA neuronal firing and BDNF, and to decrease neuroinflammation. Given the absence of side effects in our human pilot study, we are hopeful to explore a well tolerated treatment option with potential for neuroprotective as well as symptomatic benefits in PD.

2. Objectives

The primary objective of the study is to examine the effect of taVNS on motor symptoms in patients with mild to moderate motor symptoms of PD. The study design is a single site, parallel, randomized, sham controlled, double blinded study, administering taVNS vs sham stimulation 5 days a week for 2 weeks to 35 study subjects. Additional outcomes will be effects on cognition, safety assessments, as well as stimulation effects on relevant biomarkers.

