Specific Aim 1: To examine in a 2-week, randomized, sham controlled, double blind trial the effect of taVNS on motor symptoms in patients with mild to moderate motor symptoms of PD.

Hypothesis: taVNS will be superior to sham stimulation on its effects on the motor section of the Movement Disorder Society Unified Parkinson's Disease Rating Scale (MDS UPDRS; primary outcome measure).

Specific Aim 2: To examine in a 2-week, randomized, sham controlled, double blind trial the effect of taVNS on cognitive symptoms in PD.

Hypothesis: taVNS will be superior to sham stimulation on its effects on a composite score of the following cognitive assessment tools: DKEFS, Stroop, Digit symbol, Digit span forward and backwards, Fixation (control), Reflexive, and saccade inhibition tasks, CAARS, PROMIS (secondary outcome measure).

Specific Aim 3: To assess safety and tolerability of taVNS in PD.

Hypothesis: Treatment with taVNS will be as well tolerated as sham stimulation on the following parameters: acute monitoring of vital signs, MDS UPDRS motor evaluations and cognition testing to evaluate for worsening PD severity, adverse events or serious adverse events assessments, and the Columbia Suicide Severity Rating Scale (CSSRS). (tertiary outcome measure)

Specific Aim 4:(exploratory aim) To evaluate effects of taVNS versus sham stimulation on biomarkers relevant to VNS neurobiology.

Hypothesis: taVNS and not sham stimulation will lead to a decrease in serum inflammatory biomarkers (TNF-alpha, and IL-6), increase in serum BDNF, and increase in resting pupil diameter.

3. Design

Overview:

This pilot study of taVNS in PD intends to prove basic concepts of acute motor and cognition improvements with taVNS in PD patients. We will accomplish this by a two-week, single site, parallel, randomized, double blinded, sham-controlled pilot study of taVNS in 35 PD patients. There will be 1 screening visit, 10 stimulation visits, and 1 follow up visit.

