At the **screening visit** (visit SC) we will obtain informed consent, review inclusion and exclusion criteria, medical history, demographics. We will obtain a baseline MoCA exam, based on proposed exclusionary criteria. For those enrolled, medications used in the treatment of PD will be held constant throughout the study. Baseline blood draw in the amount of 3 teaspoons (<15ML) for biomarkers will be obtained by appropriately trained personnel. Urine pregnancy test will be administered to women of childbearing potential. We will randomize the patient to sham (n=15) versus active taVNS stimulation (n=15), and obtain baseline cognition battery (in normal *ON PD medication state*) at this time.

At **visit 1**, MDS UPDRS motor evaluation will be videotaped in the *OFF PD medication state* (defined as at least 12 hours without PD medication). Stimulation or sham will occur over 1 hour as defined below, and then repeat MDS UPDRS motor evaluation will be videotaped. A blinded rater will later score the modified (minus rigidity) MDS UPDRS on all videos at completion of the study.

Visits 2-4 are stimulation treatment visits in the *ON med state* with safety assessments, but no efficacy measures.

Visit 5 (study mid point) includes *OFF med* motor evaluation pre/post stimulation as at visit 1, in addition to the stimulation session.

Visit 6 is a taVNS treatment visits in the *ON med* state with additional behavioral saccade testing.

Visits 7-8 are stimulation treatment visits in the *ON med state* with safety assessments, but no efficacy measures.

Visit 9 is an *ON med* stimulation visit, and includes repeat cognition battery following the stimulation session.

Visit 10 (final day of stimulation) includes *OFF med* motor evaluation pre/post stimulation as at visit 1, in addition to the stimulation session. Repeat blood draw.

Visit 11 (Safety follow up visit) six to fourteen days after visit 10, we will check for any adverse events that might have occurred since the last stimulation session.

SCHEDULE OF ACTIVITIES

	Screening Baseline			Maintenance Phase					Follow up
	Visit SC Week 0-2 (-14d)	Visit 1 Stim day 1	Visit 2-4	Visit 5	Visit 6	Visit 7-8	Visit 9	Visit 10	+6-14 days
Written Informed Consent	x								
Eligibility Criteria	x								
MoCA	x								
Med/Neuro History	x								
Physical Exam	x								x
Blood Draw	x								
Cognitive Battery	x						x		
C-SSRS	x				x		x		
Pre-stim MDS UPDRS		x		x					x
stimulation thresholds		x							

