taVNS vs sham stimulation		x	x	x	x	x	x	x	
pupillometry		x							
saccade					x				
Vital Signs		x	x	x	x	x	x	x	
Post-stim MDS UPDRS		x		x				x	
Monitoring AE		x	x	x	x	x	x	x	x

MDS-UPDRS- Movement Disorder Society- Unified Parkinson's Disease Rating Scale (motor portion used)

C-SSRS- Columbia-Suicide Severity Rating Scale

[figure not shown]
taVNS- transauricular vagal nerve stimulation

saccade- Fixation (control), Reflexive, and saccade inhibition tasks. This is INCLUDED in cognitive battery, but will be done as a stand-alone test on stim day 6

Cognitive Battery- DKEFS, Stroop test, Digit-Symbol test, Digit Span, saccade,

Patient reported measures- CAARS, PROMIS (fatigue, sleep related, Applied Cognitive Abilities)

Figure 1: Overview of Study Flow / Assessments

4. Eligibility Criteria

Inclusion Criteria:

Age: 40-82 y
Idiopathic Parkinson's Disease Diagnosis
Disease Stage: Hoehn and Yahr stage 2-3
Patient requires a minimum of 3 doses of levodopa daily
Willingness to be videotaped

Exclusion criteria:

Dementia or MoCa <24
PD psychosis
Ear trauma
Facial pain
TBI or clinical history of stroke
Metal implants above the shoulders
History of myocardial infarction or arrhythmia, bradycardia
Active respiratory disorder
Alcohol or substance use disorders
History of DBS or other brain surgery
Epilepsy
Pregnancy
B-Blockers, dopamine blocking agent, antiarrhythmic medication, acetylcholine esterase inhibitor, midodrine, florinef, droxidopa, or anticholinergic drugs

5. Randomization and masking

Randomization of the 35 subjects will be designed to yield an expected assignment ratio of 1:1 for taVNS and sham stimulation. Treatment assignments will be masked to the patients and to all study personnel with exception of PI and others vital to providing the actual treatment. Patients will be masked to transcutaneous stimulation of the auricular branch of the vagus nerve at the tragus, versus sham stimulation. Sham stimulation involves identical perceptual threshold finding and stimulation parameters as active stimulation, with the exception of stimulation target. Sham stimulation will be delivered to the left earlobe, a target

believed to have little to no vagal nerve innervation. A blinded MUSC Movement Disorder Neurologist will rate six videotaped MDS UPDRS examinations. Rater will be blinded to sham versus active stimulation, pre-stimulation versus post-stimulation state, and to the stimulation day of study.

6. Treatment plan

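### The plan gives two randomised totals, 30 and 35, and 35 does not follow from 26 evaluable participants with about 10% attrition

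*Combined protocol and SAP*

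**What the plan says.** Four places give 35:

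- Section 2 (Objectives): "administering taVNS vs sham stimulation 5 days a week for 2 weeks to 35 study subjects".
- Section 3 (Design, overview): "sham-controlled pilot study of taVNS in 35 PD patients".
- Section 5 (Randomization and masking): "Randomization of the 35 subjects will be designed to yield an expected assignment ratio of 1:1".
- Section 12.3 (Power Analysis): "Accordingly, a sample of 35 participants will be enrolled".

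Two places give arm sizes that add to 30. The screening-visit paragraph of section 3 and section 7.1 carry the same sentence: "We will randomize the patient to sham (n=15) versus active taVNS stimulation (n=15".

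Section 12.3 also gives the inputs from which 35 is said to follow. The calculation is set up as "At 80% power and alpha=.05, using a two-tailed t-test for difference in means", with assumed changes of -3.25 on taVNS and -1 on sham and a pooled SD of 2.0. The result is "the total sample size required is 26 (13 per group". The allowance for loss is then stated: "Prior studies in this clinic have found attrition to be about 10% for short-duration clinical trials".

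**The concern.** There are two separate faults. First, the number to be randomised is 30 in some sections and 35 in others, and section 3 disagrees with itself. Second, section 12.3 presents 35 as the consequence of its evaluable number and attrition rate, although those inputs lead to a smaller number, one that agrees with the 15 + 15 stated elsewhere.

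The randomised total determines the length of the allocation list, when enrolment closes, and when the mid-enrolment and end-of-enrolment DSMB meetings in section 13.1 fall due. With both numbers in the text, stopping at 30 and continuing to 35 could each be defended as following the protocol. Section 5 leaves the principal investigator unmasked, so a single fixed target would also remove any later question about whether closure was independent of the accumulating data. Nothing in the documents suggests misuse. Finally, a reader cannot tell which evaluable number and which power were intended.

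**Working it through.** **Inputs (section 12.3, with the test also named in section 12.1).** Difference 3.25 - 1 = 2.25 points; SD 2.0; standardised difference d = 2.25/2.0 = 1.125; two-sided alpha 0.05; power 80%; attrition 10%.

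**Step 1: reproduce the plan's 26.** The normal approximation is n per arm = 2(z₀.₉₇₅ + z₀.₈₀)²/d² = 2(1.960 + 0.842)²/1.125² = 12.4, rounded up to 13. Two arms give 26, so the plan's figure reproduces.

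**Step 2: inflate for attrition.**

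- On the total: 26/(1 - 0.10) = 28.9, so 29.
- Per arm: 13/0.9 = 14.4, so 15 per arm and 30 in total. This matches the arm sizes in sections 3 and 7.1.

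**Step 3: ask what attrition 35 implies.**

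- From 35 to 26: 1 - 26/35 = 25.7%.
- From 30 to 26: 1 - 26/30 = 13.3%.
- The stated rate is about 10%.

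**Step 4: try other routes to 35.**

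- The exact two-sided t-test solves at 13.43 per arm, so 14 per arm and 28 in total. Then 28/0.9 = 31.1, so 32. Reaching 35 from 28 needs 1 - 28/35 = 20% attrition.
- Multiplying instead of dividing: 26 × 1.1 = 28.6, so 29; 28 × 1.1 = 30.8, so 31.
- Inflating 30 a second time: 30/0.9 = 33.3, so 34. That counts the allowance twice and is not described in the plan.

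None of these reaches 35.

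**Step 5: ask whether 30 and 35 could describe different populations.** If 35 were the number screened, five screen failures would reconcile the figures. Section 5 rules this out because it randomises the 35, and section 2 has all 35 receiving taVNS or sham. Nor can 15 per arm be the evaluable number: sections 3 and 7.1 attach it to the act of randomising, and section 12.3 puts the evaluable number at 13 per group.

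**Step 6: consequence for power** (exact noncentral t, d = 1.125, two-sided 0.05).

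| Randomised | Evaluable after 10% loss | Arms | Power | Difference detectable at 80% power |
|---|---|---|---|---|
| 30 | 30 × 0.9 = 27 | 14/13 | 80.2% | 2.25 points |
| 35 | 35 × 0.9 = 31.5, taken as 31 | 16/15 | 85.7% | 2.08 points |

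If each participant is lost at random with probability 10%, and power is averaged over the resulting arm sizes, it is 79.9% for 15/15 randomised and 86.0% for 18/17 randomised. For reference, 13/13 gives 78.6% and 14/14 gives 81.7%.

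**The case against.** The strongest reply is that the sections governing the number, randomisation and power, both say 35, as do the objectives and the design overview. The total of 30 is never written; it is the sum of two bracketed arm sizes in one sentence that appears twice. Most readers would take 35. That number exceeds the stated minimum of 26, so the fault in section 12.3 is a missing reason for a larger sample and not a shortfall.

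A second reply is that 30 is not firmly derived either. The plan names a t-test, and the exact t-test needs 14 per arm. Inflated for 10% loss, 14/0.9 = 15.6, so 16 per arm and 32 in total. On that reading neither 30 nor 35 is the derived total, and 30 sits right at the 80% line (79.9% when averaged over random loss).

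Both replies have some force. They limit the consequence, and they mean that 30 should be described as following from the plan's own 26, not as the only correct answer. They do not remove the contradiction: the sentence with the arm sizes is current text in two sections, the documents do not say that one number replaces the other, and no standard calculation from the stated inputs gives 35.

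**Conclusion.** The concern holds on both counts. Sections 3 (screening visit) and 7.1 randomise 30; sections 2, 3 (overview), 5 and 12.3 give 35. The stated inputs lead to 29, or 30 in equal arms (32 with the exact t-test size). The gap is five participants, and 35 would correspond to 25.7% attrition on 26, or 20% on 28, against a stated rate of about 10%.

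This does not show the trial to be underpowered. If the 2.25-point difference, the SD of 2.0 and the 10% loss are accepted as given, power is about 80% with 30 randomised and about 86% with 35. The point is the consistency and derivation of a core design number. It should be corrected, but it does not undermine the primary analysis.

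**What to change.** State one randomised total consistently in sections 2, 3, 5, 7.1 and 12.3, with arm sizes, derivation and power.

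- **If 35 is kept:** replace both n=15 entries in sections 3 and 7.1 with arm sizes that suit an odd total under a 1:1 ratio (for example 18/17). Restate section 12.3 as 35 randomised, about 31 evaluable after 10% attrition, and power of about 86% for a 2.25-point difference with SD 2.0. Alternatively, state and justify the larger attrition allowance that leads to 35.
- **If 30 is kept:** change 35 to 30 in sections 2, 3, 5 and 12.3, and state about 27 evaluable and power of about 80%.

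In either case, name the formula behind the 26. Thirteen per group is the normal-approximation size; the exact t-test gives 78.6% power there and passes 80% at 14 per group. This is a side note and does not call for more patients.

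The cost is wording only, submitted to the IRB in writing as a protocol amendment under section 14.2. The analysis does not change, and no patients are needed beyond the totals already in the plan.

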13.1 Data Safety Monitoring Board (DSMB)

An independent review committee charged to monitor the conduct of the protocol to ensure the safety of participants and the validity and integrity of the data. The DSMB will include a movement disorder neurologist, an Epilepsy Neurologist with specialized knowledge of Vagal Nerve Stimulation use.

Only the DSMB will review summary data that contains partially unblinded comparisons of AEs and outcomes. The actual study team members will be partially blinded to group assignment for portions of the study. The study reports for review by the DSMB will be prepared by the study coordinator.

Meetings will be held every prior to commencing recruitment, mid enrollment and at the end of enrollment and data collection. The study reports for review by the DSMB will be prepared by the study coordinator. Each report provides cumulative summary statistics including: 1) the number of subjects in each phase of the protocol, and the number who have completed the protocol; 2) the amount of data lost (including subject withdrawal); 3) the presence of any AE, and 4) the presence of any new information, regarding the expected efficacy and safety of taVNS.

From these data, the DSMB will make a determination of whether research progress is satisfactory, whether subjects' risk/benefit ratio has changed, and whether any changes need to be made to any protocol. The DSMB will consult with the database manager, for assurance that no breach of confidentiality has occurred and that quality control procedures are working well. The DSMB will write an annual letter stating that they have reviewed the data and approved the study to continue, that will be included in the annual IRB renewals of the protocol.

13.2 Quality assurance monitoring

The best assurance device is quality-conscious personnel. PI will meet regularly with the research staff, review data collected, and review consent documents for accuracy and completeness. In addition, staff will be reminded of their responsibilities in adhering to high ethical standards, in protecting the privacy of trial participants and confidentiality of records, and in collecting accurate data. They will be reminded to make known to proper authorities any suspicious or wrongful actions in relation to the study. Each member of the research group will sign a statement indicating knowledge and understanding of the above and to disclose potential conflicts of interest. The next best set of assurances lies in the use of design strategies that protect the results from treatment-related biases. This includes random assignment of patients to active treatment or placebo, and masked data collection and outcome assessment. Assurances also depend on the documents, and procedures used for data collection and monitoring.

13.3 Safety Plan

In the event that a participant discloses suicidal ideation or intent to harm him or herself during the formal interview (C-SSRS) or at any other time during the study visit, research staff will contact the PI as soon as possible. The PI will further assess suicidality and develop an appropriate safety plan. If at all possible, the study participant will not be left alone during this time; however, if it is necessary to leave the participant alone in order to contact the PI or enlist other resources, the time left alone will be minimized. Although not anticipated, other situations requiring immediate response from a mandated reporter (i.e., intent to harm someone else, abuse or neglect of a child or dependent adult), will be handled similarly in accordance with applicable state and federal laws.

14. Protection of Human Subjects

14.1 Human subjects

Participants will be men and women with idiopathic PD, with inclusion and exclusion criteria detailed above. There will be no restrictions to participation based on gender, race, or ethnicity. We expect to enroll participants that are representative of the ethnic and racial diversity of the geographic and patient populations of our institution (Medical University of South Carolina).

14.2 IRB approval

Notice of IRB approval and the stamped consent form are required before any study activities may begin. The IRB will be informed promptly of any changes to the study protocol. The appropriate protocol amendment and changes will be submitted to the IRB in writing. Reporting of adverse events will be done according to MUSC IRB policy. A summary adverse event data (not by treatment assignment) will be submitted on an annual basis to the IRB.

14.3 Recruitment and Consent procedures

Patients will be recruited from the Movements Disorders Program at MUSC, and local patient support groups. The MUSC Movement Disorders clinic neurologists are part of the PI's group practice, but are not members of the study team (except for the sub-I). When a patient is seen in clinic, or contacts the site expressing interest, he/she will be informed of the nature of the study by their neurologist or the study coordinator. If the patient chooses to learn more, there may be a short delay between discussing the nature of the study, and the coordinator contacting the patient for a screening visit. If the patient chooses to learn more, he/she will read the consent or have the consent read to him/her. Discussion(s) with prospective subjects will take place in private setting. The patient will then be given the opportunity to discuss the protocol and ask questions. The consent will be signed by the

participant at that time or they will agree to return for a research screening visit and sign the consent form at that time in the presence of the study coordinator. In addition to this recruitment effort, potential candidates will be contacted via telephone by the study coordinator after (or in advance of) their routine clinic visits if the patient's neurologist identifies that person as a potential participant. In this case, the neurologist will give the names of potential participants to the coordinator who will contact the patient, briefly explain the study, and assess the patient's interest. If interested, the coordinator will ask the patient to come in for a screening visit at which time the consent form will be reviewed and signed. The signed consent form will be maintained in a specific study folder in a locked file cabinet. The participant will be given a copy of the signed consent.

Those able to obtain consent include the Principal Investigator, Co-investigator(s), and site research coordinators.

This study will not include patients with dementia. However, capacity to give consent will be carefully assessed in clinical interviews of patients by study staff experienced in clinical PD research. In the course of these interviews, study staff will assess the ability of patients to:

- Comprehend the study and its consent form, by asking them to repeat the key elements of the research
- Understand the study and its consent form, by answering questions about the key elements of the research
- Appreciate the consequences of what will or could happen to them should they agree to participate
- If in this process, a potential patient is found not capable of fully providing consent for participation, then this person will be excluded from study participation

